13.2.6.3 Reporting

All AEs that occurred during this clinical study will be recorded. The start of the AE reporting for a subject will be the signing of informed consent for this study. Between the time of informed consent and with the first dose of study drug, only AEs (non-serious and serious) assessed as related to study procedures should be reported. All other events should be reported as medical history. After the first dose of study drug, all AEs (serious and non-serious, related and unrelated) should be reported. Unless a subject withdraws consent for follow-up, all subjects must be followed until the end of the AE reporting period at 7 days after the last study drug administration or when any ongoing drug-related AEs and/or SAEs have resolved or become stable. The PI should use appropriate judgment in ordering additional tests as necessary to monitor the resolution of events. The Sponsor may request that certain AEs be followed longer and/or additional safety tests be performed.

The PI or designee will review each event and assess its relationship to drug treatment (yes [related] or no [unrelated]). Each sign or symptom reported will be graded on the National

Institution of Health's Common Terminology Criteria for Adverse Events (CTCAE) version 4.03 or higher toxicity grading scale.

Grade refers to the severity of the AE. The CTCAE displays Grades 1 through 5 with unique clinical descriptions of severity for each AE based on the following general guideline [[CTCAE Jun 2010](#)]:

Grade 1	Mild; asymptomatic or mild symptoms; clinical or diagnostic observations only; intervention not indicated.
Grade 2	Moderate; minimal, local or noninvasive intervention indicated; limiting age-appropriate instrumental ADL*.
Grade 3	Severe or medically significant but not immediately life-threatening; hospitalization or prolongation of hospitalization indicated; disabling; limiting self-care ADL**.
Grade 4	Life-threatening consequences; urgent intervention indicated.
Grade 5	Death related to AE.

A Semi-colon indicates 'or' within the description of the grade.

Note: Activities of Daily Living (ADL)

* Instrumental ADL refer to preparing meals, shopping for groceries or clothes, using the telephone, managing money, etc.

** Self-care ADL refer to bathing, dressing and undressing, feeding self, using the toilet, taking medications, and not bedridden.

13.2.6.4 Serious Adverse Event

If any AEs are serious, as defined by the FDA Code of Federal Regulations (CFR), Title 21, special procedures will be followed. All SAEs will be reported to the Sponsor via fax or e-mail within one working day of becoming aware of the event, whether or not the serious events are deemed drug-related. All serious event reporting will adhere to 21 CFR 312.32 for Investigational New Drugs (IND) and to the Guidance for Industry and Investigators: Safety Reporting Requirements for INDs and BA/BE, dated December 2012. The institutional review board (IRB) will be notified of the Alert Reports as per FDA regulations.

A SAE is any AE or suspected adverse reaction that in the view of either the PI (or designee) or Sponsor, results in any of the following outcomes: Death, a life-threatening AE, inpatient hospitalization or prolongation of existing hospitalization, a persistent or significant incapacity or disability, or a congenital anomaly/birth defect. Important medical events that may not result in death, be life-threatening, or require hospitalization may be considered serious when, based upon appropriate medical judgment, they may jeopardize the patient or subject and may require medical or surgical intervention to prevent one of the outcomes

listed in the above definition. Examples of such medical events include allergic bronchospasm requiring intensive treatment in an emergency room or at home, blood dyscrasias or convulsions that do not result in inpatient hospitalization, or the development of drug dependency or drug abuse.

Life-threatening is defined as an AE or suspected adverse reaction that in the view of the PI (or designee) or Sponsor, its occurrence places the patient or subject at immediate risk of death. It does not include an AE or suspected adverse reaction that, had it occurred in a more severe form, might have caused death.

All SAEs occurring from the signing of consent through 7 days after the last dose of study drug (itraconazole / rifampin or LOXO-292, whichever comes last) must be reported on a SAE Report Form and sent by fax or e-mail to the Sponsor listed in [Section 3](#) within 24 hours of the knowledge of the occurrence.

When using the SAE efax ([contact]), a cover page including study identification number and study drug product (i.e., LOXO-292) is required. Alternatively, an email can be sent to [contact].

The PI is not obligated to actively seek information regarding the occurrence of new SAEs beginning after the 7-day postdose period. However, if the PI learns of such an SAE, and that event is deemed relevant to the use of study drug, he/she should promptly document and report the event.

The PI will be requested to supply detailed information as well as follow-up regarding the SAE. Although not considered an AE per se, the Sponsor must be notified of any subject or subject's partner who becomes pregnant during the study at any time between the start of screening until 90 days after the last administration of study drug.

13.3 Pharmacokinetic Assessments

13.3.1 Blood Sampling and Processing

For all subjects, blood samples for the determination of plasma LOXO-292 will be collected at scheduled time points as delineated in the Study Events Flow Chart ([Section 6](#)).

Instruction for blood sampling, collection, processing, and sample shipment will be provided separately.

13.3.2 Plasma Pharmacokinetic Parameters

PK parameters for plasma LOXO-292 will be calculated as follows, as appropriate:

AUC0-24: The area under the concentration-time curve, from time 0 to the 24 hours postdose Day 1, as calculated by the linear trapezoidal method (for Part 2, Day 1 PK only).

AUC0-t:	The area under the concentration-time curve, from time 0 to the last observed non-zero concentration, as calculated by the linear trapezoidal method.
AUC0-inf:	The area under the concentration-time curve from time 0 extrapolated to infinity. AUC0-inf is calculated as the sum of AUC0-t plus the ratio of the last measurable plasma concentration to the elimination rate constant.
AUC%extrap:	Percent of AUC0-inf extrapolated, represented as $(1 - AUC0-t/AUC0-inf) * 100$.
Cmax:	Maximum observed concentration.
CL/F:	Apparent total plasma clearance after oral (extravascular) administration, calculated as Dose/AUC0-inf.
Tmax:	Time to reach Cmax. If the maximum value occurs at more than one time point, Tmax is defined as the first time point with this value.
Kel:	Apparent first-order terminal elimination rate constant calculated from a semi-log plot of the plasma concentration versus time curve. The parameter will be calculated by linear least-squares regression analysis using the maximum number of points in the terminal log-linear phase (e.g., three or more non-zero plasma concentrations).
t ^{1/2} :	Apparent first-order terminal elimination half-life will be calculated as $0.693/Kel$.

No value for Kel, AUC0-inf, or t^{1/2} will be reported for cases that do not exhibit a terminal log-linear phase in the concentration-time profile. The sampling to 24 hours for Day 1 PK in Period 2, Part 2 may not be sufficient for calculation of several Kel-dependent PK parameters.

No PK parameters will be calculated for subjects with 2 or fewer consecutive time points with detectable concentrations.

Individual and mean plasma concentration time curves (both linear and log-linear) will be included in the final report.

13.3.3 Analytical Method

Samples will be analyzed for plasma LOXO-292 using validated bioanalytical methods. Samples from subjects to be assayed are specified in [Section 14.2](#).

13.4 6 β -Hydroxycortisol to Free Cortisol Ratio Assessment (Part 2 Only)

For future potential assessment of CYP enzyme induction in Period 2 of Part 2, morning urine will be collected as delineated in the Study Events Flow Chart ([Section 6](#)) and may be measured for 6 β -hydroxycortisol and free cortisol concentrations.

Prior to the predose sample, each subject will be instructed as to urine collection methods.

Instructions for urine sampling, collection, processing, and sample shipment will be provided in a separate document.

Samples will be stored and may be analyzed in the future if deemed necessary by the Sponsor.

13.5 Blood Volume Drawn for Study Assessments

13.5.1 Part 1

Table 3: Blood Volume during the Study (Itraconazole DDI)

Sample Type	Number of Time Points	Approximate Volume per Time Point * (mL)	Approximate Sample Volume Over Course of Study (mL)
Screening laboratory safety tests (including hematology, serum chemistry, serology, and coagulation), FSH (for postmenopausal female subjects only), thyroid stimulating hormone, and serum pregnancy (for female subjects only).	1	16	16
On-study hematology, coagulation, serum chemistry (includes serum pregnancy for female subjects only when scheduled at the same time)	6 up to 7	16	96 up to 112
Blood for LOXO-292	39 up to 40	4	156 up to 160
Total Blood Volume (mL)→			268 up to 288 **

* Represents the largest collection tube that may be used for this (a smaller tube may be used).

** If additional safety or PK analysis is necessary or if larger collection tubes are required to obtain sufficient plasma/serum for analysis, additional blood may be obtained (up to a maximum of 50 mL).

13.5.2 Part 2

Table 4: Blood Volume during the Study (Rifampin DDI)

Sample Type	Number of Time Points	Approximate Volume per Time Point * (mL)	Approximate Sample Volume Over Course of Study (mL)
Screening laboratory safety tests (including hematology, serum chemistry, serology, and coagulation), FSH (for postmenopausal female subjects only), thyroid stimulating hormone, and serum pregnancy (for female subjects only).	1	16	16
On-study hematology, coagulation, serum chemistry (this includes serum pregnancy for female subjects only when scheduled at the same time)	7 up to 8	16	112 up to 128
Blood for LOXO-292	53 up to 54	4	212 up to 216
Total Blood Volume (mL)→			340 up to 360 **

* Represents the largest collection tube that may be used for this (a smaller tube may be used).

** If additional safety or PK analysis is necessary or if larger collection tubes are required to obtain sufficient plasma/serum for analysis, additional blood may be obtained (up to a maximum of 50 mL).

14 STATISTICAL CONSIDERATIONS

Data will be handled and processed according to Celerion Standard Operating Procedures, which are written based on the principles of GCP.

14.1 Sample Size Determination

CCI subjects in each study part are considered sufficient to evaluate the magnitude of the DDI.

14.2 Population for Analyses

PK Population: Samples from all subjects will be assayed even if the subjects do not complete the study. All subjects who comply sufficiently with the protocol and display an evaluable PK profile (e.g., exposure to treatment, availability of measurements and absence of major protocol violations) will be included in the statistical analyses.

Safety Population: All subjects who received at least one dose of LOXO-292 will be included in the safety evaluations.

14.3 Statistical Analyses

Detailed methodology for summary and statistical analyses of the data collected in this study will be documented in a Statistical Analysis Plan (SAP). The SAP will be prepared by Celerion and agreed upon with the Sponsor. This document may modify the plans outlined in the protocol; however, any major modifications of the primary endpoints definition and/or its analysis will also be reflected in a protocol amendment. Additional statistical analyses other than those described in this section may be performed if deemed appropriate.

14.3.1 Pharmacokinetic Analyses

14.3.1.1 Descriptive Statistics

Plasma concentrations of LOXO-292 and the PK parameters listed in Section 13.3.2 will be summarized using the appropriate descriptive statistics to be fully outlined in the SAP.

14.3.1.2 Analysis of Variance

An ANOVA will be performed on the ln-transformed AUC0-t, AUC0-24 (for Part 2, Day 1 PK only), AUC0-inf, and Cmax. The ANOVA model will include treatment and period as fixed effects and subject as a random effect. Each ANOVA will include calculation of LSM as well as the difference between treatment LSMs.

In Part 1, data of the sentinel subjects will be included in the analysis if the same LOXO-292 dose (160 mg) was administered in the remaining subjects.

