10 STUDY DESIGN

10.1 Overall Study Design and Plan

This is a 2-part study. Each part will be conducted as an open label, 2-period, fixed-sequence study. Study parts may be conducted concurrently. Subjects will only participate in one study part.

CCI [REDACTED] healthy, adult male and female (women of non-childbearing potential only) subjects will be enrolled in total; CCI [REDACTED] to each study part (Parts 1 and 2). Every attempt will be made to enroll at least 4 subjects of each sex in each study part.

Screening of subjects will occur within 28 days prior to the first dosing.

Part 1 (Itraconazole):

On Day 1 of Period 1, a single oral dose of LOXO-292 will be administered followed by PK sampling for 168 hours.

In Period 2, an oral dose of itraconazole will be administered QD for 11 consecutive days (Day -4 to Day 7) with a single oral dose of LOXO-292 coadministered on Day 1. Pharmacokinetic sampling for LOXO-292 will be taken for 168 hours following LOXO-292 dosing on Day 1.

A CCI [REDACTED] will initiate Part 1; all subjects will receive a single dose of LOXO-292 on Day 1 of both periods. Following collection of the last PK sample in Period 2, the PI, in consultation with the Sponsor, will review all pertinent safety and tolerability data before proceeding to dose the remaining subjects.

Interim PK will be provided after completion of the sentinel group but it is not required for the dose selection of the remaining subjects.

There will be a washout period of at least 7 days between the dose in Period 1 and the first dose (i.e., itraconazole) in Period 2.

Safety will be monitored throughout the study.

Timing of all study procedures are indicated in the Study Events Flow Chart (Section 6, Table 1)

Part 2 (Rifampin):

On Day 1 of Period 1, a single oral dose of LOXO-292 will be administered followed by PK sampling for 168 hours.

In Period 2, an oral dose of rifampin will be administered QD for 16 consecutive days (Days 1 to 16) with a single oral dose of LOXO-292 coadministered on Day 1 and Day 10.

Pharmacokinetic sampling for LOXO-292 will be taken for 24 hours following LOXO-292 dosing on Day 1 and for 168 hours following LOXO-292 dosing on Day 10.

Morning urine will be collected on Days 1, 4, 8, and 10 of Period 2 (and will be stored for future potential assessment of 6 β -hydroxycortisol and free cortisol concentrations to evaluate the level of CYP3A enzyme induction).

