12 TREATMENTS

12.1 Treatments Administered

LOXO-292 will be supplied as a 20 mg or 80 mg capsules.

Itraconazole will be supplied as 100 mg capsules.

Rifampin will be supplied as 300 mg capsules.

Treatments are described as follows:

Part 1 (Itraconazole, Sentinel subjects CCI

Treatment A (Period 1): 160 mg LOXO-292 (2 x 80 mg[§] capsules) at Hour 0 on Day 1.

Treatment B (Period 2): 200 mg itraconazole (2 x 100 mg capsules) administered approximately every 24 hours from Day -4 to Day 7 (within ± 1 hour of dosing time on Day -4), with 160 mg LOXO-292 (2 x 80 mg[§] capsules) coadministered at Hour 0 on Day 1.

Part 1 (Itraconazole, Remaining subjects CCI

Treatment A (Period 1): 160 mg LOXO-292 (2 x 80 mg[§] capsules)* at Hour 0 on Day 1.

Treatment B (Period 2): 200 mg itraconazole (2 x 100 mg capsules) administered approximately every 24 hours from Day -4 to Day 7 (within ± 1 hour of dosing time on Day -4), with 160 mg LOXO-292 (2 x 80 mg[§] capsules)* coadministered at Hour 0 on Day 1.

On Day 1 of both Periods 1 and 2, study drug(s) will be administered following an overnight fast. On all other dosing days in Period 2, itraconazole will be administered approximately 30 minutes after the start of a standard breakfast. All study drugs will be administered with approximately 240 mL of water.

[§] The 2 x 80 mg capsules may be substituted for 8 x 20 mg capsules. If the study drugs cannot all be swallowed at the same time, the drug administration may be divided; however, dosing should be completed within 10 minutes. Additional water, up to a maximum of 50 mL may be administered as required by the subject.

* Following completion of the sentinel group, the PI and Sponsor will review all pertinent safety and tolerability data from the sentinel group before proceeding to dose the remaining subjects.

Part 2 (Rifampin CCI

Treatment C (Period 1): 160 mg LOXO-292 (2 x 80 mg[§] capsules) at Hour 0 on Day 1.

Treatment D (Period 2): 600 mg rifampin (2 x 300 mg capsules) administered approximately every 24 hours on Day 1 to Day 16 (within \pm 1 hour of dosing time on Day 1), with 160 mg LOXO-292 (2 x 80 mg[§] capsules) coadministered at Hour 0 on Day 1 and Day 10.

All study drugs will be administered orally under fasting conditions, with approximately 240 mL of water.

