14.3.1.3 Ratios and Confidence Intervals

Ratios of LSMS will be calculated using the exponentiation of the difference between treatment LSMS from the analyses on the ln-transformed AUC0-t, AUC0-24 (for Part 2, Day 1 PK only), AUC0-inf, and Cmax. These ratios will be expressed as a percentage relative to the appropriate reference treatment.

Consistent with the two one-sided tests [Schuirmann, 1987], 90% confidence interval (CI) for the ratios will be derived by exponentiation of the CIs obtained for the difference between treatment LSMS resulting from the analyses on the ln-transformed AUC0-t, AUC0-24 (for Part 2, Day 1 only), AUC0-inf, and Cmax. The CIs will be expressed as a percentage relative to the appropriate reference treatment.

The comparisons of interest are as follows:

- Treatment B compared with Treatment A [Part 1]
- Treatment D (Day 1 dosing) compared with Treatment C [Part 2]
- Treatment D (Day 10 dosing) compared with Treatment C [Part 2]

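### The primary PK model fits treatment and period together in a fixed-sequence design, so none of the three planned comparisons is estimable as written

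*Protocol*

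**What the plan says.** Section 10.1 of the protocol describes the design: "Each part will be conducted as an open label, 2-period, fixed-sequence study". Section 12.1 ties every treatment to one period. For Part 1 it lists "Treatment A (Period 1): 160 mg LOXO-292" and "Treatment B (Period 2): 200 mg itraconazole"; for Part 2, "Treatment C (Period 1): 160 mg LOXO-292" and "Treatment D (Period 2): 600 mg rifampin". Treatment D contains two LOXO-292 doses, on Day 1 and Day 10, both inside Period 2. No section adds a second sequence.

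Section 14.3.1.2 then sets the model for the log-transformed parameters: "The ANOVA model will include treatment and period as fixed effects and subject as a random effect". Treatment least-squares means (LSMs) and their differences are to come from this model. Section 14.3.1.3 exponentiates those differences into ratios with 90% confidence intervals for three comparisons: B with A, D (Day 1) with C, and D (Day 10) with C. Section 8.2.3 names AUC0-t, AUC0-inf, Cmax and, for Part 2 Day 1 only, AUC0-24 as the primary endpoints.

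Section 14.3 allows the SAP to modify the plan, but adds that "any major modifications of the primary endpoints definition and/or its analysis will also be reflected in a protocol amendment".

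**The concern.** A period term can be separated from treatment only if some subjects receive the treatments in a different order. Here nobody does, and each planned comparison sets a Period 2 treatment against a Period 1 treatment. The model is therefore asked to split one observed shift into a treatment part and a period part, with nothing in the data to split it by.

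At stake are the primary ratios and intervals of both parts, which cannot be obtained from the model as specified. What an analyst gets instead depends on how the program handles a redundant term. A period term also suggests to a reader that the ratios are adjusted for period, which this design cannot do.

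**Working it through.** The protocol gives no figure to reproduce: the number of subjects is redacted, and no power or precision is stated. The check is one of estimability, and its result does not depend on the number of subjects.

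**Inputs.** Model terms from section 14.3.1.2; allocation of treatments to periods from sections 10.1 and 12.1; contrasts from section 14.3.1.3.

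**Part 1.** Write μ for the intercept, τ for treatment and π for period. Only two expected values are ever observed:

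- A: μ + τ_A + π_1
- B: μ + τ_B + π_2

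An estimable function must be a combination a·(first) + b·(second). To obtain τ_B − τ_A we need a = −1 and b = 1, which gives (τ_B − τ_A) + (π_2 − π_1). The period difference does not cancel. The LSM for A is μ + τ_A + (π_1 + π_2)/2. It needs a = 1 and b = 0, but that carries π_1 with weight 1 rather than ½. Neither quantity is estimable.

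**Part 2, treatment at three levels.** The observed expectations are:

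- C: μ + τ_C + π_1
- D Day 1: μ + τ_D1 + π_2
- D Day 10: μ + τ_D10 + π_2

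Both contrasts against C carry π_2 − π_1. Only D (Day 10) − D (Day 1) is free of period, and it is not a planned comparison.

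**Numerical confirmation.** For each design matrix X (intercept, treatment, period), a contrast L is estimable only if L = L(X′X)⁻(X′X). The protocol does not say whether Part 2 is one three-level model or two pairwise models, nor whether three dosing occasions might be coded as three periods, so all were tried.

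| Model | Columns | Rank with period | Rank without | Estimable with period |
|---|---|---|---|---|
| Part 1 | 1 + 2 + 2 = 5 | 2 | 2 | neither LSM, not B − A |
| Part 2, three levels, two periods | 1 + 3 + 2 = 6 | 3 | 3 | only D10 − D1 |
| Part 2, C with one D occasion | 1 + 2 + 2 = 5 | 2 | 2 | no LSM, no contrast |
| Part 2, three occasions as periods | 1 + 3 + 3 = 7 | 3 | 3 | no LSM, no contrast |

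The result is the same for 6, 12 and 20 subjects and with subject columns added (for 12 subjects, rank 13 in Part 1 and 14 in the three-level Part 2 model, with or without period). It also holds in Part 1 when two subjects lack Period 2 data. A random subject effect does not help, because subjects do not differ in sequence.

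**Degrees of freedom left for treatment after period.** Intercept plus period has rank 2. Treatment therefore keeps 2 − 2 = 0 degrees of freedom in Part 1. In the three-level Part 2 model it keeps 3 − 2 = 1, which is the Day 10 versus Day 1 contrast.

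**After deleting period.** All LSMs and all three planned contrasts become estimable. As an illustration only, assume 12 subjects per part and a within-subject CV of 20% to 40%. The Part 1 90% limits are the point ratio multiplied by exp(±t(0.95, 11)·√ln(1 + CV²)·√(2/12)). The multipliers are 0.865 to 1.156 at 20%, 0.806 to 1.240 at 30% and 0.754 to 1.326 at 40%.

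**The case against.** The best defence is that this is a slip in stating the model and does not harm the study. The comparisons, the log scale, the exponentiated differences and the 90% level are all specified correctly, and the data lose no information when period goes. Section 14.3 leaves detailed methods to the SAP and lets it modify the protocol, and dropping a term that adds no rank may not count as a major modification. A non-estimable flag in the output would be noticed. A program that drops period would return the intended treatment-only analysis. In Part 1, even dropping treatment would leave a Period 2 minus Period 1 difference numerically equal to B minus A.

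Much of this stands. The design is sound, and the unseen SAP may already have the right model. How any particular program behaves was not tested here; the clearest room for a misleading coefficient is the three-level Part 2 model, where treatment keeps one degree of freedom that is not a planned contrast. AUC0-24 also applies only to Part 2 Day 1, so not every parameter enters every comparison.

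None of it makes the sentence correct. Section 14.3.1.1 defers descriptive statistics to the SAP, whereas section 14.3.1.2 names the model terms outright and gets them wrong. The same sentence appears in the April 2018 protocol and in Amendments 1 and 2. A primary result should not depend on which redundant column a program discards.

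**Conclusion.** The concern holds. Under the stated model, all three planned comparisons and all treatment LSMs are non-estimable for each parameter to which they apply. Counting parameters per comparison (three for B with A, four for D Day 1 with C, three for D Day 10 with C) gives at most 3 + 4 + 3 = 10 ratios with intervals. The maximum may not be reached, because section 13.3.2 warns that Kel-dependent parameters may not be calculable from the 24-hour Day 1 profile.

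The conclusion rests only on the single sequence per part and on the model as written. It needs no assumption about sample size, variability or dropout. It concerns the stated analysis and does not invalidate the design or the data. The model must be corrected before the primary analysis is run.

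**What to change.** In section 14.3.1.2, delete period. Specify treatment as the only fixed effect (levels A and B in Part 1; C, D Day 1 and D Day 10 in Part 2) with subject as a random effect. Add one sentence saying that treatment and period cannot be separated in a fixed-sequence design, so the ratios assume no period effect and the study cannot test that assumption.

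Make sure the SAP carries the same model. The sponsor should decide and record whether section 14.3 requires a protocol amendment for this; the protocol text needs correcting in either case. The synopsis names no model terms and can stay as it is.

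The cost is a wording change. Dosing, sampling, subject numbers and procedures are unaffected, and no rank or information is lost.
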